## **7.3 SOURCE DATA DOCUMENTATION**

Study monitors will perform ongoing source data verification to confirm that critical protocol data (i.e., source data) entered into the eCRFs by authorized site personnel are accurate, complete, and verifiable from source documents.

Source documents (paper or electronic) are those in which patient data are recorded and documented for the first time. They include, but are not limited to, hospital records, clinical and office charts, laboratory notes, memoranda, patient-reported outcomes, evaluation checklists, pharmacy dispensing records, recorded data from automated instruments, copies of transcriptions that are certified after verification as being accurate and complete, microfiche, photographic negatives, microfilm or magnetic media, X-rays, patient files, and records kept at pharmacies, laboratories, and medico-technical departments involved in a clinical trial.

Before study initiation, the types of source documents that are to be generated will be clearly defined in the Trial Monitoring Plan. This includes any protocol data to be entered directly into the eCRFs (i.e., no prior written or electronic record of the data) and considered source data.

Source documents that are required to verify the validity and completeness of data entered into the eCRFs must not be obliterated or destroyed and must be retained per the policy for retention of records described in Section 7.5.

To facilitate source data verification, the investigators and institutions must provide the Sponsor direct access to applicable source documents and reports for trial-related monitoring, Sponsor audits, and IRB/EC review. The study site must also allow inspection by applicable health authorities.

## **7.4 USE OF COMPUTERIZED SYSTEMS**

When clinical observations are entered directly into a study site's computerized medical record system (i.e., in lieu of original hardcopy records), the electronic record can serve

as the source document if the system has been validated in accordance with health authority requirements pertaining to computerized systems used in clinical research. An acceptable computerized data collection system allows preservation of the original entry of data. If original data are modified, the system should maintain a viewable audit trail that shows the original data as well as the reason for the change, name of the person making the change, and date of the change.

## **7.5 RETENTION OF RECORDS**

Records and documents pertaining to the conduct of this study and the distribution of IMP, including eCRFs, PRO data (if applicable), Informed Consent Forms, laboratory test results, and medication inventory records, must be retained by the Principal Investigator for at least 15 years after completion or discontinuation of the study, or for the length of time required by relevant national or local health authorities, whichever is longer. After that period of time, the documents may be destroyed, subject to local regulations.

No records may be disposed of without the written approval of the Sponsor. Written notification should be provided to the Sponsor prior to transferring any records to another party or moving them to another location.

## **8. ETHICAL CONSIDERATIONS**

### **8.1 COMPLIANCE WITH LAWS AND REGULATIONS**

This study will be conducted in full conformance with the ICH E6 guideline for Good Clinical Practice and the principles of the Declaration of Helsinki, or the laws and regulations of the country in which the research is conducted, whichever affords the greater protection to the individual. The study will comply with the requirements of the ICH E2A guideline (Clinical Safety Data Management: Definitions and Standards for Expedited Reporting). Studies conducted in the United States or under a U.S. Investigational New Drug application will comply with U.S. FDA regulations and applicable local, state, and federal laws. Studies conducted in the European Union (E.U.) or European Economic Area will comply with the E.U. Clinical Trial Directive (2001/20/EC).

### **8.2 INFORMED CONSENT**

The Sponsor's sample ICF for study participation and an ICF for the Historical Data Collection (i.e., the collection of data for the off-treatment period between studies TRO19622CLEQ1275-1 and TRO19622CLEQ1115-1 and screening for study BN29854 and ancillary sample Informed Consent Forms such as a Child's Informed Assent Form or Home Nursing Informed Consent Form, if applicable) will be provided to each site. If applicable, ICFs will be provided in a certified translation of the local language. The Sponsor or its designee must review and approve any proposed deviations from the Sponsor's sample ICFs or any alternate consent forms proposed by the site (collectively, the "Consent Forms") before IRB/EC submission. The final IRB/EC-approved Consent

Forms must be provided to the Sponsor for health authority submission purposes according to local requirements.

If applicable, the ICF will contain separate sections for any optional procedures. The investigator or authorized designee will explain to each patient the objectives, methods, and potential risks associated with each optional procedure. Patients will be told that they are free to refuse to participate and may withdraw their consent at any time for any reason. A separate, specific signature will be required to document a patient's agreement to participate in optional procedures. Patients who decline to participate will not provide a separate signature.

The Consent Forms must be signed and dated by the patient or the patient's legally authorized representative before his or her participation in the study. The case history or clinical records for each patient shall document the informed consent process and that written informed consent was obtained prior to participation in the study.

At applicable sites, patients might receive the visit of a HN for drug delivery and selected procedures, if the patient has given written informed consent to participate in HN visits.

The Consent Forms should be revised whenever there are changes to study procedures or when new information becomes available that may affect the willingness of the patient to participate. The final revised IRB/EC-approved Consent Forms must be provided to the Sponsor for health authority submission purposes.

Patients must be re-consented to the most current version of the Consent Forms (or to a significant new information/findings addendum in accordance with applicable laws and IRB/EC policy) during their participation in the study. For any updated or revised Consent Forms, the case history or clinical records for each patient shall document the informed consent process and that written informed consent was obtained using the updated/revised Consent Forms for continued participation in the study.

A copy of each signed Consent Form must be provided to the patient or the patient's legally authorized representative. All signed and dated Consent Forms must remain in each patient's study file or in the site file and must be available for verification by study monitors at any time.

### **8.3 INSTITUTIONAL REVIEW BOARD OR ETHICS COMMITTEE**

This protocol, the Informed Consent Forms, any information to be given to the patient, and relevant supporting information must be submitted to the IRB/EC by the Principal Investigator and reviewed and approved by the IRB/EC before the study is initiated. In addition, any patient recruitment materials must be approved by the IRB/EC.

The Principal Investigator is responsible for providing written summaries of the status of the study to the IRB/EC annually or more frequently in accordance with the requirements,

policies, and procedures established by the IRB/EC. Investigators are also responsible for promptly informing the IRB/EC of any protocol amendments (see Section 9.6).

In addition to the requirements for reporting all adverse events to the Sponsor, investigators must comply with requirements for reporting serious adverse events to the local health authority and IRB/EC. Investigators may receive written IND safety reports or other safety-related communications from the Sponsor. Investigators are responsible for ensuring that such reports are reviewed and processed in accordance with health authority requirements and the policies and procedures established by their IRB/EC, and archived in the site's study file.

#### **8.4 CONFIDENTIALITY**

The Sponsor maintains confidentiality standards by coding each patient enrolled in the study through assignment of a unique patient identification number. This means that patient names are not included in data sets that are transmitted to any Sponsor location.

Patient medical information obtained by this study is confidential and may be disclosed to third parties only as permitted by the Informed Consent Form (or separate authorization for use and disclosure of personal health information) signed by the patient, unless permitted or required by law.

Medical information may be given to a patient's personal physician or other appropriate medical personnel responsible for the patient's welfare, for treatment purposes.

Data generated by this study must be available for inspection upon request by representatives of national and local health authorities, Sponsor monitors, representatives, and collaborators, and the IRB/EC for each study site, as appropriate.

#### **8.5 FINANCIAL DISCLOSURE**

Investigators will provide the Sponsor with sufficient, accurate financial information in accordance with local regulations to allow the Sponsor to submit complete and accurate financial certification or disclosure statements to the appropriate health authorities. Investigators are responsible for providing information on financial interests during the course of the study and for 1 year after completion of the study (i.e., LPLV).

### **9. STUDY DOCUMENTATION, MONITORING, AND ADMINISTRATION**

#### **9.1 STUDY DOCUMENTATION**

The investigator must maintain adequate and accurate records to enable the conduct of the study to be fully documented, including but not limited to the protocol, protocol amendments, Informed Consent Forms, and documentation of IRB/EC and governmental approval. In addition, at the end of the study, the investigator will receive

the patient data, including an audit trail containing a complete record of all changes to data.

## **9.2 PROTOCOL DEVIATIONS**

The investigator should document and explain any protocol deviations. The investigator should promptly report any deviations that might have an impact on patient safety and data integrity to the Sponsor and to the IRB/EC in accordance with established IRB/EC policies and procedures. *The Sponsor will review all protocol deviations and assess whether any represent a serious breach of Good Clinical Practice guidelines and require reporting to health authorities. As per the Sponsor's standard operating procedures, prospective requests to deviate from the protocol, including requests to waive protocol eligibility criteria, are not allowed.*

## **9.3 SITE INSPECTIONS**

Site visits will be conducted by the Sponsor or an authorized representative for inspection of study data, patients' medical records, and eCRFs. The investigator will permit national and local health authorities, Sponsor monitors, representatives, and collaborators, and the IRBs/ECs to inspect facilities and records relevant to this study.

## **9.4 ADMINISTRATIVE STRUCTURE**

The Sponsor of the trial is F. Hoffmann-La Roche Ltd. The Sponsor is responsible for the study management (monitoring), medical oversight, data management, statistical analysis, and medical writing for the Clinical Study Report.

An IxRS system will be used to register the screening/screening failures, enrolment, withdrawal, discontinuation, and completion of patients and for management of study drug inventory at trial sites.

A central laboratory will be used to provide sample kits to all sites and collect samples for the assessments listed in Section 4.4.8 and Section 4.4.19.

A central ECG laboratory will be used to assess all ECG tracings.

External consultants will provide training to site staff on various scales and assessments to ensure standardization across sites.

At applicable sites, certain study assessments may be performed by an HN professional at the patient's home to improve access and convenience for patients participating in the study.

The Sponsor will select a healthcare company that will be responsible for providing HN services for participating sites (the HN vendor). The HN vendor is responsible for ensuring that all HN professionals are licensed, qualified, and in good standing, as per applicable regulations, and that appropriate background checks have been performed. If

the investigator at a participating site determines that HN services are appropriate for a patient and the patient gives written informed consent to participate in HN visits, the HN network will communicate with the patient and the patient's site. HN visits will be scheduled on specified visit days, to allow for relevant assessments to be performed by the HN professional.

## **9.5 PUBLICATION OF DATA AND PROTECTION OF TRADE SECRETS**

Regardless of the outcome of a trial, the Sponsor is dedicated to openly providing information on the trial to healthcare professionals and to the public, both at scientific congresses and in peer-reviewed journals. The Sponsor will comply with all requirements for publication of study results. For more information, refer to the Roche Global Policy on Sharing of Clinical Trials Data at the following Web site:

*[http://www.roche.com/roche\\_global\\_policy\\_on\\_sharing\\_of\\_clinical\\_study\\_information.pdf](http://www.roche.com/roche_global_policy_on_sharing_of_clinical_study_information.pdf)*

The results of this study may be published or presented at scientific congresses. For all clinical trials in patients involving an IMP for which a marketing authorization application has been filed or approved in any country, the Sponsor aims to submit a journal manuscript reporting primary clinical trial results within 6 months after the availability of the respective clinical study report. In addition, for all clinical trials in patients involving an IMP for which a marketing authorization application has been filed or approved in any country, the Sponsor aims to publish results from analyses of additional endpoints and exploratory data that are clinically meaningful and statistically sound.

The investigator must agree to submit all manuscripts or abstracts to the Sponsor prior to submission for publication or presentation. This allows the Sponsor to protect proprietary information and to provide comments based on information from other studies that may not yet be available to the investigator.

In accordance with standard editorial and ethical practice, the Sponsor will generally support publication of multicenter trials only in their entirety and not as individual center data. In this case, a coordinating investigator will be designated by mutual agreement.

Authorship will be determined by mutual agreement and in line with International Committee of Medical Journal Editors authorship requirements. Any formal publication of the study in which contribution of Sponsor personnel exceeded that of conventional monitoring will be considered as a joint publication by the investigator and the appropriate Sponsor personnel.

Any inventions and resulting patents, improvements, and/or know-how originating from the use of data from this study will become and remain the exclusive and unburdened property of the Sponsor, except where agreed otherwise.

## **9.6            PROTOCOL AMENDMENTS**

Any protocol amendments will be prepared by the Sponsor. Protocol amendments will be submitted to the IRB/EC and to regulatory authorities in accordance with local regulatory requirements.

Approval must be obtained from the IRB/EC and regulatory authorities (as locally required) before implementation of any changes, except for changes necessary to eliminate an immediate hazard to patients or changes that involve logistical or administrative aspects only (e.g., change in Medical Monitor or contact information).

### Schedule of Assessments

	Screen. a	Baseline	Treatment Period										Dose Increase Visit b, c	SFU Dose Increase Visit c	Unsched. Visit d	Treat. Comp./Early Discont. e	Safety Follow-Up f
Visit			V1	V2	V3	V4	V5	V6	V7	V8	V9	V N e					
Week (Window; days)	–42 to –1	1	13 (± 7)	26 (± 7)	39 (± 7)	52 (± 7)	78 (± 14)	104 (± 14)	130 (± 14)	156 (± 14)	Every 26 weeks e	(± 14)	(+ 28 days after dose increase visit) (± 5)				(+ 28 days after last dose) (± 5)
Informed consent	x g											x					
History data collection h	x																
Demographic data	x																
Medical history	x																
Weight i		x	x	x	x	x	x	x	x	x	x	x			x		
Height i		x		x		x	x	x	x	x	x	x			x		
Physical examination j	x	x	x	x	x	x	x	x	x	x	x	x		x	x		
Vital signs k	x	x	x	x	x	x	x	x	x	x	x	x		x	x		
Tanner staging l		x				x		x		x	(x) l						
Safety laboratory assessments m	x	x	x	x	x	x	x	x	x	x	x	x	x	x	x	x	

**Appendix 1**  
**Schedule of Assessments (cont.)**

	Screen. a	Baseline	Treatment Period									Dose Increase Visit b, c	SFU Dose Increase Visit c	Unsched. Visit d	Treat. Comp./Early Discont. e	Safety Follow-Up f
Visit		V1	V2	V3	V4	V5	V6	V7	V8	V9	V N e					
Week (Window; days)	-42 to -1	1 (± 7)	13 (± 7)	26 (± 7)	39 (± 7)	52 (± 7)	78 (± 14)	104 (± 14)	130 (± 14)	156 (± 14)	Every 26 weeks e (± 14)	(+ 28 days after dose increase visit) (± 5)				(+ 28 days after last dose) (± 5)
Hormone assessments h		x				x		x		x	(x) h	x			x	
Pregnancy test o	x	x	x	x	x	x	x	x	x	x	x	x			x	
Urinalysis p	x				x			x		x	(x) h	x			x	
PK assessment q		x	x	x	x	x	x	x	x	x	x r	x	x		x	
SMN2 protein and SMN2 mRNA q, s		x	x	x			x		x	x	x	x				
Fluid biomarker q, t		x	x	x			x		x	x	x	x				
Clinical genotyping q, u		x								x c		x				
ECG v	x		x		x w		x w		x w	(x)					x	
Holter ECG c											x	x				
PedsQL x	x		x		x	x	x	x	x	x					x	
EQ-5D-5L x	x		x		x	x	x	x	x	x					x	
Caregiver Reported Outcomes y	x		x		x	x	x	x	x	x					x	

**Appendix 1**  
**Schedule of Assessments (cont.)**

	Screen. a	Baseline	Treatment Period									Dose Increase Visit b, c	SFU Dose Increase Visit c	Unsched. Visit d	Treat. Comp./Early Discont. e	Safety Follow-Up f
Visit		V1	V2	V3	V4	V5	V6	V7	V8	V9	V N e					
Week (Window; days)	–42 to –1	1 (± 7)	13 (± 7)	26 (± 7)	39 (± 7)	52 (± 7)	78 (± 14)	104 (± 14)	130 (± 14)	156 (± 14)	Every 26 weeks e (± 14)	(+ 28 days after dose increase visit) (± 5)				(+ 28 days after last dose) (± 5)
CGI-C c						x	x	x				x				
OFS c												x				
SMAIS c				x		x	x	x	x	x	x			x		
MFM		x		x		x	x	x	x	x	x				x	
FVC		x		x		x	x	x	x	x	x				x	
IMP dispensation		x	x	x	x	x	x	x	x	x	x					
Concomitant medications	x	x	x	x	x	x	x	x	x	x	x	x	x	x	x	
Adverse events z		x	x	x	x	x	x	x	x	x	x	x	x	x	x	x
Telephone calls aa																
RCR mRNA and plasma sample bb		x				x		x								
RCR DNA bb		x														

## Appendix 1

### Schedule of Assessments (cont.)

	Screen. a	Baseline	Treatment Period									Dose Increase Visit b, c	SFU Dose Increase Visit c	Unsched. Visit d	Treat. Comp./Early Discont. e	Safety Follow-Up f
Visit		V1	V2	V3	V4	V5	V6	V7	V8	V9	V N e					
Week (Window; days)	–42 to –1	1 (± 7)	13 (± 7)	26 (± 7)	39 (± 7)	52 (± 7)	78 (± 14)	104 (± 14)	130 (± 14)	156 (± 14)	Every 26 weeks e (± 14)	(+ 28 days after dose increase visit) (± 5)				(+ 28 days after last dose) (± 5)
Digital biomarker remote assessment c, cc																→
Digital biomarker in-clinic assessment c, cc		x		x		x	x	x	x	x	x			x		

CGI-C = Clinical Global Impression of Change; Comp. = Completion; Discont. = Discontinuation; eCRF = electronic Case Report Form; EQ-5D-5L = EuroQol 5-Dimension, 5-Level Questionnaire; FVC = Forced Expiratory Vital Capacity; HN = home nursing; IMP = investigational medicinal product; MFM = Motor Function Measure; OFS = Olesoxime Fatigability Survey; PedsQL = Pediatric Quality of Life Inventory; PK = pharmacokinetic; PRO = patient-reported outcome; RCR = Roche Clinical Repository; SFU = Safety Follow-Up; Screen. = Screening; SMAIS = SMA Independence Scale; Treat. = Treatment; Unsched. = Unscheduled.

## Appendix 1

### Schedule of Assessments (cont.)

Notes: All assessments should be performed within 14 days of the scheduled visit, unless otherwise specified. *Laboratory safety samples should preferably be collected first at each visit under fasting conditions.* Following food, the PRO assessments (in the pre-specified order) should be administered first. Then, all other assessment can be performed in the order convenient for the patient and site. *If it is not possible for the patient to perform all assessments during the day, the site may divide the assessments between 2 consecutive days.*

The following assessments may be performed by an HN professional: vital signs, urine pregnancy test, all lab assessments, and IMP dispensation.

- a Screening can be prolonged up to 6 weeks for relevant clinical, administrative, or operational reasons. Results of standard-of-care tests or examinations performed prior to obtaining informed consent and within 7 days prior to Day 1 may be used; such tests do not need to be repeated for screening.
- b *Dose increase visit can be performed either at next scheduled visit or at unscheduled visit (as described in Section 3.1.1.4).*
- c *Procedures should only be performed by patients that consent to Protocol BN29854, Version 4.*
- d Unscheduled visit: If the patient reports new or worsening of symptoms related to the disease or an adverse event, the treating physician can request that the patient come for a clinical visit for further assessment or monitoring. Assessments should be performed as clinically indicated.
- e The open-label treatment period can terminate at any time (please refer to End of Study Section 3.2). When the study is ended for a particular country, a completion visit should occur as soon as possible but no later than 6 weeks after study end. Patients who discontinue study drug prematurely will return to the clinic for a treatment discontinuation visit 28 ( $\pm 5$ ) days after the last dose of study drug. The assessments requested for Visit *N* represent the typical schedule of assessments during a scheduled visit.
- f Required follow-up information will be collected via a phone call. An unscheduled follow-up visit may occur if the treating investigator deems it necessary.
- g Informed consent must be documented before any study-specific screening procedure is performed and may be obtained more than 28 days before initiation of study treatment. Please note that there is a separate consent form for historical data collection and for the open-label treatment period of the study. Please refer to Section 4.4.1.
- h Refer to Appendix 2 and Section 4.4.2 (Historical Data Collection).
- i Anthropometric measurement as described in Section 4.4.4.
- j At screening, includes evaluation of the head, eyes, ears, nose, and throat, and the cardiovascular, dermatologic, musculoskeletal, respiratory, gastrointestinal, genitourinary, and neurologic systems. At subsequent visits, limited, symptom-directed physical examinations should be performed. At baseline visit, record abnormalities observed *during* screening and *at* baseline on the General Medical History and Baseline Conditions eCRF. After baseline visit, record new or worsened clinically significant abnormalities on the Adverse Event eCRF. Please refer to Section 4.4.5.
- k Includes respiratory rate, pulse rate, and systolic and diastolic blood pressures while the patient is in a seated position, and temperature. Vital signs should be measured prior to blood draw or at least 10 minutes after the last blood draw. Record abnormalities on the Adverse Event eCRF.

## Appendix 1

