## **2.1 PRIMARY OBJECTIVE**

The primary safety objective for this study is as follows:

- To evaluate the safety of olesoxime in patients with SMA, focusing on the nature, frequency, and severity of adverse events, as well as effects on laboratory values, vital signs and electrocardiogram (ECG) parameters

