### **5.3.1 Adverse Event Reporting Period**

Investigators will seek information on adverse events at each patient contact. All adverse events, whether reported by the patient or noted by study personnel, will be recorded in the patient's medical record and on the Adverse Event eCRF.

**After informed consent** has been obtained **but prior to initiation of study drug**, only serious adverse events caused by a protocol-mandated intervention (e.g., invasive procedures such as biopsies, discontinuation of medications) should be reported (see Section 5.4.2 for instructions for reporting serious adverse events).

**After initiation of study drug**, all adverse events will be reported until 28 days after the last dose of study drug. After this period, the investigator should report any serious adverse events that are believed to be related to prior study drug treatment (see Section 5.6).

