### **5.3.5.5 Abnormal Vital Sign Values**

Not every vital sign abnormality qualifies as an adverse event. A vital sign result must be reported as an adverse event if it meets any of the following criteria:

- Is accompanied by clinical symptoms
- Results in a change in study treatment (e.g., dosage modification, treatment interruption, or treatment discontinuation)
- Results in a medical intervention or a change in concomitant therapy
- Is clinically significant in the investigator's judgment

It is the investigator's responsibility to review all vital sign findings. Medical and scientific judgment should be exercised in deciding whether an isolated vital sign abnormality should be classified as an adverse event.

If a clinically significant vital sign abnormality is a sign of a disease or syndrome (e.g., high blood pressure), only the diagnosis (i.e., hypertension) should be recorded on the Adverse Event eCRF.

Observations of the same clinically significant vital sign abnormality from visit to visit should only be recorded once on the Adverse Event eCRF (see Section 5.3.5.3 for details on recording persistent adverse events).

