## **6.6 PRIMARY ANALYSES**

Safety analysis will be based on the safety population.

Safety variables (e.g., laboratory tests, vital signs, and ECG) will be summarized for each assessment time (including follow-up) using descriptive statistics. *The data will be summarized by the dose being taken at the time of the assessment (10 mg/kg QD or 10 mg/kg BID). Data from the two 24-hour Holter ECG assessments will also be summarized.*

Adverse events will be coded and summarized by body system and preferred term. Adverse events will also be summarized by intensity and relationship to trial treatment as assigned by the investigator. Serious adverse events will be summarized separately. *Adverse events will be summarized by the dose being taken at the onset date of the adverse event.*

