4.6.2 Adverse Events

For each adverse event (AE) recorded, the term entered by the investigator describing the event (the 'verbatim term') will be assigned to a standardized term (the 'preferred term') based on the most up-to-date version of MedDRA. Data displays of AEs will be performed using the system organ class and preferred terms. For summaries of AE incidences, patients who experienced the same event on more than one occasion will be counted once in the calculation of the event frequency at the highest intensity reported. Each table will also present the overall number of patients experiencing at least one AE and the total number of AEs reported.

AEs will be summarized for the following analysis periods separately:

Treatment period: includes (a) the AEs for which the onset date is on or after the first day of the study drug up to 28 days after the last dose day; or (b) the AEs for which the onset date is prior to the first dose day with the end date on or after the first dose day or the AE is unresolved, and the most extreme intensity is greater than the initial intensity.

Overall AEs, AEs reported in ≥ 5% of patients, AEs by intensity, AEs leading to death, serious AEs (SAEs), AEs leading to withdrawal of study treatment, AEs leading to dose modification or interruption, AEs related to study treatment (as assigned by the treating investigator), and SAEs related to study treatment will be summarized. SAEs reported in ≥ 1% of patients may also be summarized.

Follow-up period: includes the serious AEs for which the onset date is 29 days or more after the last dose day and that the investigator believes to be related to prior study drug treatment.

In addition, non-treatment emergent AEs, including the SAEs caused by a protocol-mandated intervention (e.g. invasive procedures such as biopsies, discontinuation of

medications) for which the onset date is before the date of the start of study medication, will be listed.

The following rules will be applied for AEs with missing onset and/or end dates:

- Events that are missing both onset and end dates will be considered treatment emergent, given that a patient had at least one dose of study drug.
- If the onset date is missing and the end date is on or after the first dosing date, then the event will be considered treatment emergent.
- If the end date is missing and the onset date is on or after the first dosing date, then the event will be considered treatment emergent.

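### Appendix 1 footnote k sends vital-sign abnormalities to the adverse event form without condition, while Sections 5.3.5.5 and 5.3.1 set limits, so adverse event counts in the primary analysis depend on which passage a site follows

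*Protocol*

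**What the plan says.** Footnote k belongs to the vital signs row of the Appendix 1 schedule: temperature, respiratory rate, pulse rate, and systolic and diastolic pressure. After instructions on how to measure, it ends: "Record abnormalities on the Adverse Event eCRF". It does not define an abnormality, exempts no visit, and does not refer to any other section.

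Protocol Section 5.3.5.5 is the dedicated rule for vital signs. It opens: "Not every vital sign abnormality qualifies as an adverse event". Reporting is required if the reading comes with symptoms, changes study treatment, leads to an intervention or a change in other therapy, or is clinically significant in the investigator's view. It adds: "Medical and scientific judgment should be exercised in deciding whether an isolated vital sign abnormality should be classified as an adverse event".

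For the time between consent and first dose, Section 5.3.1 says that "only serious adverse events caused by a protocol-mandated intervention" should be reported. Footnote z of Appendix 1 repeats this.

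Adverse events carry the primary objective, which is safety, "focusing on the nature, frequency, and severity of adverse events" (Section 2.1). In the primary analysis, "Adverse events will be coded and summarized by body system and preferred term" (Section 6.6), split by the dose taken at onset. SAP Section 4.6.2 adds: "Each table will also present the overall number of patients experiencing at least one AE and the total number of AEs reported".

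**The concern.** A site cannot follow footnote k and Section 5.3.5.5 literally at the same time. An isolated reading outside the normal range, with no symptoms and no consequence, goes on the adverse event form under the footnote. Under the section it does so only if the investigator judges it clinically significant. The schedule is what staff have in hand at a visit, and its notes also allow vital signs to be taken by home nurses.

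The study has about 23 sites in 7 countries, no concurrent control and no hypothesis test, so its primary result is a set of descriptive adverse event tables. If sites record the same reading differently, those tables partly describe which instruction was read.

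**Working it through.** The plan gives no figure to reproduce: sample size is set by enrolment from the earlier studies. The check is mainly a comparison of texts.

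**1. The recording rules side by side**

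| Place | Findings covered | Condition for an adverse event entry |
|---|---|---|
| Appendix 1, footnote k | Vital signs at every scheduled visit | None |
| Section 5.3.5.5 | Vital signs | Any of four criteria; judgment for isolated readings |
| Section 5.3.1 and footnote z | Anything before first dose | Serious, and caused by a protocol-required procedure |
| Appendix 1, footnote j | Physical examination | After baseline: "record new or worsened clinically significant abnormalities on the Adverse Event eCRF"; screening and baseline findings go to medical history |

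Footnote j, directly above, carries the limits that footnote k lacks, which suggests an oversight. Section 4.4.6, on vital signs, gives no recording rule and does not settle the matter.

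**2. Which entries reach the treatment-period tables**

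SAP Section 4.6.2 assigns events by date.
- Screening readings: an event with onset before the first dose day counts only if it continues to that day or is unresolved, and also worsens in intensity. These would rarely enter.
- Day 1 readings taken before the dose: onset on the first dose day counts as treatment period. If baseline and first dose fall on the same day, a pre-dose reading entered under footnote k could count as treatment-emergent.
- Later readings: all count.

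The quantities affected are total adverse events, patients with at least one event, and vital-sign preferred terms.

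**3. Illustration of scale**

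Inputs: 5 signs (footnote k); 8 post-baseline visits to Week 156 (V2 to V9, Appendix 1), hence 5 × 8 = 40 readings per patient. Assumption, not in the documents: each reading is abnormal with probability p = 1% to 5%, independently.

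- At least one abnormal reading at a visit, 1 − (1 − p)^5: 1 − 0.99^5 = 4.9%; 1 − 0.95^5 = 22.6%.
- At least one by Week 156, 1 − (1 − p)^40: 1 − 0.99^40 = 33%; 1 − 0.95^40 = 87%.
- By Week 104 (6 visits, 30 readings): 1 − 0.99^30 = 26%; 1 − 0.95^30 = 79%. With the maximum of 171 patients all followed to Week 104, abnormal readings number 171 × 30 × p, about 51 to 256.

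These are upper-end values. Readings within a patient are correlated, Section 5.3.5.5 has the same abnormality recorded only once across visits, and an unknown share would meet one of the four criteria anyway.

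**4. What the illustration does not measure**

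Let b be the share of patients with some other adverse event and s the share with a vital-sign entry that does not meet 5.3.5.5. If the two are independent, the rise in patients with any adverse event is (1 − b) × s. The documents give neither b nor s for this study. In the earlier randomised trial 38.2% of patients had a serious event alone (Protocol Section 1.2.2), so b is unlikely to be small, and the rise would be well below s.

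**The case against.** The best defence is that Section 5.3 already tells investigators to record adverse events according to its own instructions, and that section holds a specific vital-sign rule. The general definition in Section 5.2.1 also expects a worsened clinical test to bring symptoms or a change in treatment. On this view footnote k is loose shorthand, and nothing shows that any site reads it literally. The schedule's adverse event row has no mark at screening, and footnote z restates the pre-dose limit in the same appendix. The SAP has separate tables for serious, related, fatal and treatment-modifying events, which isolated readings would mostly leave untouched. SAP Section 4.6.5 reports out-of-range vital signs in any case.

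Most of this stands as a limit on the harm. It does not remove the conflict: no passage ranks one instruction above the other, and the footnote is written as a plain order.

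A reader might infer three stronger things that the documents do not support.
- That 5.3.5.5 treats most abnormalities as non-events. It says only that not every one qualifies, and gives no proportion.
- That a third or more of patients would be wrongly counted as having an adverse event. The 33% to 87% rests on an assumed rate and independent readings, and is not a net increase.
- That real signals would be diluted or the comparison of dose periods biased. Tabulation by preferred term keeps such entries largely apart, and the conflict alone gives no reason for a site's habit to differ between once-daily and twice-daily dosing.

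**Conclusion.** The contradiction is in the current text and should be corrected. Footnote k conflicts with Section 5.3.5.5 at every visit and with Section 5.3.1 and footnote z before first dose. Where a site follows it, readings that do not qualify enter total adverse events, patients with at least one event and vital-sign preferred terms in the primary safety tables. Pre-dose readings matter mainly on Day 1.

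The effect cannot be sized from the documents. The illustrative range depends wholly on the assumed 1% to 5% rate and on independence. With no hypothesis test, the damage is to the consistency and readability of descriptive counts, not to an error rate. It is a modest defect, but it touches the primary analysis and is cheap to remove.

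**What to change.** Replace the last sentence of footnote k with: 'Before first dose, record clinically relevant abnormalities on the General Medical History and Baseline Conditions eCRF; after first dose, record on the Adverse Event eCRF only abnormalities that meet the criteria in Section 5.3.5.5.' Notify sites, including home nursing staff, that Sections 5.3.5.5 and 5.3.1 govern. Serious pre-dose events caused by a protocol-required procedure stay reportable under 5.3.1.

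The cost is one sentence and a notice. No vital-sign data are lost: SAP Section 4.6.5 already summarises the values, lists those out of range and provides shift tables.

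There is one small downside. The sentence does not appear to be marked as new in Version 4, so entries may already have been made under it. If recording changed only from now on, the change would coincide with the move from once-daily to twice-daily dosing and could itself distort the by-dose tables. Existing vital-sign entries should therefore be reviewed against 5.3.5.5, so that one rule applies to both dose periods.
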